### **I. Research Objectives/Background**

As of 2017, cigarette smoking remained the leading cause of preventable premature death worldwide and the CDC predicts tobacco use will result in more than 8 million deaths per year by 2030. Tobacco use disorder (TUD), like other drugs of abuse, is associated with deficits in prefrontal mediated inhibitory control (IC)—the ability to stop pre-potent behavioral responding. We recently reported findings in JAMA Psychiatry showing that IC task-based functional connectivity (tbFC) between the right inferior frontal gyrus (r.IFG) and thalamus (corticothalamic circuit) mediated the association between IC task performance (i.e. successful trial inhibition) and smoking relapse vulnerability: both in a smoking cessation study and delaying to initiate ad lib smoking in the laboratory. Those findings form the basis of our current work examining brain stimulation strategies to strengthen corticothalamic tbFC, improve IC and increase the odds of smoking abstinence among smokers.

Theta burst stimulation (TBS), a form of repetitive transcranial magnetic stimulation effecting areas stimulated and associated networks, is administered in two forms: a) Intermittent TBS (iTBS) which induces long-term potentiation—putatively strengthening network activity, and b) Continuous TBS (cTBS) which induces long-term depression—putatively dampening network activity. In our crossover pilot study with smokers ( $N=12$ ), participants underwent a baseline fMRI visit while performing an IC task to obtain baseline performance and identify the IC-task related peak cluster in the r.IFG for stimulation in two subsequent TBS experimental visits: 1) iTBS and 2) cTBS (order counterbalance), each 15 min. prior to performing the IC task. A significant effect of condition on IC performance was observed ( $F= 9.49$ ,  $p<.03$ ) where, as compared to baseline, performance: a) improved by 14.4% following r.IFG iTBS ( $D = .81$ ); b) worsened by -8.7% following r.IFG cTBS ( $D = .5$ ); resulting in a total performance difference between the r.IFG TBS conditions of 25.3% ( $D = 1.56$ ). These findings build on the extant literature on the role of the r.IFG in IC, demonstrate feasibility of using single-subject task-related brain activation to administer focal brain stimulation to modulate IC and provides the foundation for this proposal to examine whether: a) r.IFG TBS parametrically modulates corticothalamic tbFC (strengthen

following iTBS; weaken following cTBS); and b) iTBS-induced strengthening of corticothalamic tbFC reduces smoking lapse / relapse vulnerability. In the UG3 component, we will conduct an assessment of the acute effects of TBS on corticothalamic IC-tbFC, IC task performance and ad lib smoking in the laboratory.

The Specific aims and corresponding hypotheses of the UG3 proposal are as follows:

**Aim 1.** Examine the effects of TBS on IC neural circuitry and task performance. **Hypothesis 1:** As compared to baseline: r.IFG iTBS stimulation will strengthen corticothalamic tbFC and improve IC task performance; whereas r.IFG cTBS simulation will weaken corticothalamic tbFC and result in worse IC task performance.

**Aim 2.** Examine the effects of TBS on ad lib smoking. **Hypothesis 2:** As compared to baseline: r.IFG iTBS, will extend the duration of abstinence; whereas cTBS shorten the duration of abstinence during an ad lib smoking lapse paradigm in the lab.

**Aim 3.** Examine safety and tolerability of administering r.IFG TBS. **Hypothesis 3:** r.IFG TBS will have a similar overall adverse event profile in a TUD population as previously reported with dorsolateral prefrontal cortex TMS.

**Exploratory Aims.** Using MR Spectroscopy, the effects of TBS on r.IFG excitatory/inhibitory neurochemical balance (glutamate/GABA) will be examined. Effects of TBS on craving and mood will be explored.

*If the milestone of the UG3 component are met, the subsequent UH3 project will be an adequately powered two-week trial with two-week follow-up to assess the efficacy of iTBS in TUD.*

**Overall rationale for our research approach.** The research proposed here builds upon our novel findings demonstrating that corticothalamic tbFC mediates IC and smoking relapse vulnerability [1], and our preliminary data showing that targeting the corticothalamic circuit with TBS parametrically modulates IC in a biologically relevant, stimulation-dependent manner. The experimental design for the proposed research will address a number of important unanswered questions, including—*Does r.IFG TBS:*

- a) Modulate corticothalamic circuitry in a dose-dependent manner? (Aim 1)
- b) Modulate IC task performance in a dose-dependent manner? (Aim 1)
- c) Attenuate lapse / relapse rates? (Aim 2)
- d) Produce effects in neural mechanisms that correspond with effects in behavior (Aim 1 & 2)?
- e) Have a good safety and tolerability profile? (Aim 3)
- f) Modulate r.IFG neurochemistry? (Exploratory Aim)
- g) Modulate primary symptoms associated with TUD e.g. craving and mood? (Integrated throughout)

## **II. Drugs/Biologics/Devices**

The MagPro X100 TMS Therapy System is indicated for the treatment of Major Depressive Disorder in adult patients who have failed to receive satisfactory improvement from prior

antidepressant medication in the current episode. It is a [510K/Pre-market Notification](#) device (a device that is substantially equivalent to a legally marketed device), as described in [21 CFR 807 Subpart E](#).

### **III. Recruitment Process**

Participants will include 40 adult nicotine dependent smokers (age 18-65; Female = 50%), recruited through the community and our advertising campaigns, individuals interested in participating will undergo a phone screen or complete a REDCap survey to determine eligibility and those who meet study criteria will be invited to our lab for a screening visit. Individuals will be screened by trained and certified research staff, asked to read and sign an IRB-approved informed consent and then be assessed on smoking and medical history and administered an MRI safety screening questionnaire. Participants meeting all selection criteria will be scheduled for subsequent sessions. *Full inclusion/exclusion criteria* are provided in the appropriate section below. Briefly, inclusion criteria include: participants will be 18-65 yrs. of age; smoke > 10 cigarettes/day for  $\geq$  2 yrs.; and have an expired carbon monoxide (CO) concentration of  $\geq$  10 ppm, using a handheld CO monitor (Vitalograph, Lenexa, KS). Briefly, exclusion criteria include: use of psychotropic (e.g. antiepileptic) medications in the last month; positive urine illicit drug screen; presence of an untreated medical illness; history of major neurological illness or head injury resulting in loss of consciousness; and any contraindication to MRI; and among females, positive urine pregnancy test. Participants meeting all selection criteria will be scheduled for subsequent sessions.

We will recruit participants from Columbia and the surrounding area in which MU is located. Participants will be recruited through IRB-approved advertisements in regional newspapers, flyers, and on internet sites affiliated with our laboratory and the university. These advertisements will briefly describe the study and ask interested individuals to contact the study coordinator or designated study staff. Following IRB approved procedures, the coordinator or designated study staff member will discuss the basics of the study and basic required principles of informed consent. If the potential participant remains interested, the coordinator or designated study staff member will ask focused screening questions using an IRB-approved phone script to see if the potential participant meets entry criteria. If they appear to be eligible, and continue to be interested in the study, he or she will be scheduled for an in-person screening visit. If not, they will be thanked for their interest. We will work within IRB requirements to assure Privacy Regulations are met.

### **IV. Consent Process**

We will obtain formal written consent from all new participants enrolled in this project. Following policies of the MU IRB, written informed consent will be obtained and documented by the study's Research Coordinator or designated study staff before any study-related procedures are performed. Informed consent will be obtained in a private research office. A study coordinator or designated study staff member will review study procedures and the consent form with each potential participant. Each individual may take as much time as they like to decide if they do or do not wish to participate. A decision not to participate will not affect their participation in other studies at MU, nor will it affect their access to health care at MU.

## V. Inclusion/Exclusion Criteria

*Inclusion Criteria: Subjects will:*

1. Be between the ages of 18 and 65.
2. Be in stable mental and physical health.
3. Be willing to provide informed consent.
4. Be able to comply with protocol requirements and likely to complete all study procedures.
5. Be a current nicotine dependent cigarette smoker (smoke  $\geq 10$  cigs/day) with a minimum smoking history of smoking an average of  $\geq 10$  cigs/day over the past two years.

*Exclusion Criteria: Subjects with:*

1. Contraindication to MRI (e.g., presence of metal in the skull, orbits or intracranial cavity, claustrophobia).
2. Contraindication to TMS (history of neurological disorder or seizure, increased intracranial pressure, brain surgery, or head trauma with loss of consciousness for  $> 15$  minutes, implanted electronic device, metal in the head, or pregnancy, as indicated by a positive urine pregnancy test at screening).
3. Any use of substances that lower seizure threshold (such as thyroid medications or cocaine).
4. History of autoimmune, endocrine, viral, or vascular disorder affecting the brain.
5. History or MRI evidence of neurological disorder that would lead to local or diffuse brain lesions or significant physical impairment.
6. Unstable cardiac disease, uncontrolled hypertension, severe renal or liver insufficiency, or sleep apnea.
7. BAC greater than 0.0.
8. Any other condition or concern that in the Investigator's opinion would impact participant safety, compliance with study instructions, or potentially confound the interpretation of the study results.

As part of exclusion criteria, participants are specifically asked to not take part in any other research during their active participation in the protocol once eligibility at screening is made through the last visit day of the protocol.

[figure not shown]
## VI. Number of Subjects

*Human Subjects Involvement and Characteristics.* We propose to enroll 40 participants that meet inclusion/exclusion criteria in order to obtain 30 complete usable datasets.

TARGETED/PLANNED ENROLLMENT: 40			
Ethnic Category	Sex/Gender		
	Females	Males	Total
Hispanic or Latino	2	2	4
Not Hispanic or Latino	18	18	36
Ethnic Category: Total of All Subjects*	40		
Racial Categories			
American Indian/Alaska Native	0	0	0
Asian	1	1	2
Native Hawaiian or Other Pacific Islander	0	0	0
Black or African American	9	9	18
White	9	9	18
Other	1	1	2
Racial Categories: Total of All Subjects*	20	20	40

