## VII. Study Procedures and Research Design

The UG3 phase is a proof-of-concept study to test mechanistic hypotheses of the acute effects of TBS on corticothalamic inhibitory control (IC) task-based functional connectivity (tbFC), IC task performance and ad lib smoking in the laboratory while preliminarily evaluating safety and tolerability of TBS among individuals with TUD. Clearly defined milestones, focused on iTBS

versus cTBS and baseline on IC circuitry, will be met before proceeding to Phase 2 (UH3), a 4-session (over 2-weeks) randomized iTBS versus cTBS trial to assess smoking behavior over two-weeks post-treatment period.

As shown in Fig. 1, individuals ( $N=30$ ) with TUD will complete a baseline MRI visit and, using a crossover design, be randomly assigned to receive iTBS on one visit and cTBS on the other visit. Following TBS, they will repeat the protocol and then perform the SRT [4]. The effects of TBS on IC brain and behavior and smoking on the SRT, along with safety and tolerability, will be assessed.

**Strategies to Ensure a Robust and Unbiased Approach.** As detailed throughout this section, the proposed study will achieve robust and unbiased results via several design features including: explicit inclusion/exclusion criteria; randomization and blinding; use of validated measures; explicit hypotheses and well-validated analytic strategies; power estimates; and careful consideration of potential confounds. As standard practice in our laboratory, we will maximize participant retention and data collection compliance, while maximizing fidelity by providing participants with training on all task procedures prior to data collection.

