**Aim 1. Examine the effects of iTBS on IC neural circuitry and task performance.**

**Hypothesis 1:** As compared to baseline: r.IFG iTBS stimulation will strengthen corticothalamic tbFC and improve IC task performance; whereas r.IFG cTBS simulation will weaken corticothalamic tbFC and result in worse IC task performance. **Behavioral analysis plan:** Following procedures outlined in C.4.a, IC performance data will be analyzed with a repeated-measures ANOVA to examine the effects of Condition (Baseline, iTBS, cTBS). **fMRI data analysis plan:** Following procedures in C.4.b—C.4.d, IC corticothalamic tbFC will be processed and modeled using our validated strategy [4] and then Fisher-transformed correlation coefficients (rZ) scores for each participant during each condition will be fed forward and analyzed in SPSS using a repeated-measures ANOVA to examine the effect of Condition.

**Aim 2. Examine the effects of iTBS on ad lib smoking.** **Hypothesis 2:** As compared to baseline: r.IFG iTBS, will extend the duration of abstinence; whereas cTBS shorten the duration of abstinence during an ad lib smoking lapse paradigm in the lab. **Behavioral analysis plan:** As in [4], time to initiate ad lib smoking during the SRT (see C.4.a.2) will be analyzed in SPSS using a repeated-measures ANOVA to examine the effect of Condition. Main effects of Condition on secondary smoking topography variables (e.g. puff volume (ml) and number of puffs) will be explored.

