**Data acquisition:** At each visit, the MRS acquisition voxel ( $25 \times 25 \times 30 \text{ mm}^3$ ) will be placed in the r.IFG to correspond to the brain tissue directly underneath the TMS coil (Fig. 3). Following placement of 6 saturation bands parallel to the voxel faces and auto-shimming, single-voxel water-suppressed  $^1\text{H}$ -MRS spectra will be acquired via HERMES (TR=2000ms; TE=80ms; number of averages=320) using editing pulse frequencies for GABA and GSH acquisition (1.9 [ON GABA], 4.56 [ON GSH], and 7.5 ppm [OFF] [73]; and a PRESS sequence maximally sensitive to glutamate (TR=2000ms; TE=40ms; number of averages=128 [74]. Unsuppressed water spectra will be acquired for each sequence. **Data analysis:** Skull stripping and whole brain tissue-type segmentation will be performed on MP-RAGE images using FMRIB software [75]. In-house MATLAB functions will be used to extract the 3D volume corresponding to the positioned MRS voxel to obtain within-voxel gray matter (GM), white matter (WM) and cerebrospinal fluid (CSF) tissue content for each subject. GM/WM ratios will be used as covariates in all statistical analyses. Eddy currents and residual water will be removed using in-house MATLAB functions. HERMES data will be analyzed using the Gannet MATLAB toolbox [76]. PRESS data will be analyzed using LCModel 6.3 [77]. Metabolites with fitting uncertainties  $<20\%$  will be retained.

Water will be quantified from a Gaussian-Lorentzian fit to the non-water-suppressed data. Within-voxel tissue fractions of gray and white matter and cerebrospinal fluid will be calculated based on automated segmentation in SPM 12 using a volume mask generated in Gannet [78]. Metabolite concentrations will be normalized to unsuppressed water and corrected for within-voxel CSF fraction. Cramer-Rao Lower Bound (CRLB) values will be provided by the ProFit software and only estimates with CRLB values < 20% will be submitted to further analysis. Estimated metabolite peak areas will be normalized to the unsuppressed water signal. Finally, metabolite/water, along with metabolite/creatinine, ratios will be corrected for within-voxel CSF fraction [79]. Glutamate, glutamine, and GABA ratios will be entered into HLM models with a priori contrasts to examine differences in metabolite concentrations following r.IFG iTBS vs cTBS and baseline. Associations between metabolite concentrations and corticothalamic tbFC, IC and smoking on the SRT will be examined.

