**Missing Data and Attrition.** Missing data in repeated-measures study designs are problematic but can be minimized by effective communication between staff and participants and minimizing participant burden via maintaining a relatively compact study duration. The study team has significant experience with ensuring a robust and unbiased approach and minimizing missing data (See C.8)

*Screening/Training Visit:* During screening, all aspects of the study will be described to participants and informed consent will be acquired. Participants will provide demographic and employment history via self-report forms. Then, participants will be asked to provide breath samples to test 1) expired carbon monoxide (CO) and 2) an estimate of blood alcohol content (BAC). Additionally, urine samples will be obtained in order to assess pregnancy status and to screen for illicit drug use. Among females, the pregnancy screen will be conducted prior to the drug screen. If the result of the pregnancy test is positive, participants will not be screened for drug use or undergo any further study procedures. The results of the drug test will be recorded primarily for data analysis purposes and cocaine will be the only exclusionary illicit substance. After biological screening is complete, participants will complete medical and smoking history, MRI safety, and contact information forms and will be verbally guided through a timeline follow-back of cigarettes and other tobacco products. Participants who meet all selection criteria will be provided with the option to continue onto the training phase of the visit. During training, participants will learn and practice the inhibitory control (IC) task and fill out commonly used questionnaires that assess state and trait mood and cognitive processes (see Appendix).

*Experimental Baseline Visit:* At this visit, participants will first: provide an expired breath CO sample in order to assess recent smoking; and, among females, provide a urine sample in which the pregnancy test must be negative. Next, breath alcohol levels will be assessed with a handheld breathalyzer and participants must record a BAL of 0.0. If participants continue to be eligible after the biological samples, they will complete study questionnaires to assess mood and to characterize smoking-related behavior. After this, participants will move on to the first fMRI scan followed by the SRT task.

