## **XII. Data Safety Monitoring Plan**

This UG3 phase is a proof-of-concept study to test mechanistic hypotheses of the acute effects of theta bursts stimulation (TBS) on corticothalamic inhibitory control (IC) task-based functional connectivity (tbFC), IC task performance and ad lib smoking in the laboratory (smoking relapse task: SRT [4]), and while preliminarily evaluating safety and tolerability of TBS among individuals with TUD. Adults smokers meeting criteria for TUD (N =40) will complete a baseline MRI visit and, using a crossover design, be randomly assigned to receive iTBS on one visit and cTBS on the other visit. Following TBS, they will repeat the MRI protocol and then perform the SRT. The effects of TBS on IC brain and behavior and smoking on the SRT, along with safety and tolerability during each visit will be assessed.

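### Aims 1 and 2 rest on a three-condition repeated-measures ANOVA with no rule for partial data; a mixed model would keep whatever usable sessions incomplete participants have, for a gain between none and about 18% of variance

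*Combined protocol and SAP*

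**What the plan says.** Section VI sets enrolment at 40 "in order to obtain 30 complete usable datasets".

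In Section VII, the Aim 1 behavioural plan states that "IC performance data will be analyzed with a repeated-measures ANOVA to examine the effects of Condition (Baseline, iTBS, cTBS"). The Fisher-transformed connectivity scores "will be fed forward and analyzed in SPSS using a repeated-measures ANOVA to examine the effect of Condition". For Aim 2, time to start smoking on the SRT "will be analyzed in SPSS using a repeated-measures ANOVA to examine the effect of Condition. Main effects of Condition on secondary smoking topography" variables is the accompanying exploratory step.

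The paragraph headed Missing Data and Attrition says: "Missing data in repeated-measures study designs are problematic but can be minimized by effective communication between staff and participants". It continues with participant burden and staff experience. It names no analysis set, deletion rule, imputation or likelihood-based method for these outcomes.

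A hierarchical model does appear in the plan, but only for the exploratory spectroscopy data: "Glutamate, glutamine, and GABA ratios will be entered into HLM models with a priori contrasts".

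The number reaching Baseline is given two ways. Section VII has 30 individuals who "with TUD will complete a baseline MRI visit and, using a crossover design, be randomly assigned to receive iTBS on one visit"; Section XII has "Adults smokers meeting criteria for TUD (N =40) will complete a baseline MRI visit".

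**The concern.** The ANOVA needs all three condition values from each person. Someone who attends Baseline and one TBS visit and then stops has supplied a within-person TBS-versus-Baseline difference, which is exactly what Hypotheses 1 and 2 are about, and the standard ANOVA discards it. The plan allows for a quarter of participants to be incomplete but does not say how their data are handled.

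Two things are at stake. One is precision on the Aim 1 and Aim 2 contrasts, which Section VII says will inform the decision to proceed to UH3. The other is bias: if the people who fail to complete differ in their observed earlier results, completers' changes from Baseline need not represent everyone's. Aim 3 exists because tolerability at this stimulation site is still to be established, so loss after a TBS visit is a real possibility.

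**Working it through.** **Planned numbers.** 40 − 30 = 10, and 10/40 = 25%. Conversely 30/(1 − 0.25) = 40, so the figures agree. The plan states no loss rate, so 25% is back-calculated.

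**Assumptions for precision.** Unit variance, the same correlation r between any two conditions (compound symmetry), r = 0.3, 0.5 or 0.7. None of these is in the documents. Variances are generalised least squares with the covariance treated as known; estimating it would reduce the gains slightly.

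**Complete cases (30).** The variance of any pairwise contrast is 2(1 − r)/30. At r = 0.5 this is 0.0333.

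**Pattern A: the 10 have no usable session.** Nothing is added. Gain 0%.

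**Pattern B: the 10 have Baseline only.**
- TBS − Baseline: variance = (1 − r²)/30 + (1 − r)²/40. Relative to 2(1 − r)/30, the reduction is (1 − r)/8, which is 8.75%, 6.25% and 3.75% at r = 0.3, 0.5 and 0.7.
- iTBS − cTBS: no information added, 0%.

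**Pattern C: the 10 have Baseline plus one TBS visit, 5 with iTBS and 5 with cTBS.**
- iTBS − cTBS: variance = 2(1 − r)/[30 + 5/(1 + r)]. The bracket is the equivalent number of complete participants: 33.8, 33.3 and 32.9. Reductions are 11.4%, 10.0% and 8.9%.
- TBS − Baseline: by symmetry, variance = Var(iTBS − cTBS)/4 + Var(m − Baseline), where m is the mean of the two TBS conditions. At r = 0.5 the information is 58.33 for Baseline, 73.33 for m and −36.67 for the cross term, with determinant 2933.3. So Var(m − Baseline) = (58.33 + 73.33 − 73.33)/2933.3 = 0.01989. The total is 0.0300/4 + 0.01989 = 0.0274, against 0.0333: a reduction of 17.8%. At r = 0.3 and 0.7 the reductions are 18.4% and 17.4%, equivalent to 36.8 and 36.3 complete participants.

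**Illustration of power.** The background section gives D = 0.5 for cTBS against baseline in the pilot. Read as a paired standardised effect (an assumption), two-sided alpha 0.05, power for TBS − Baseline is 75.4% with 30 complete cases, 77.1–79.4% under B and 83.4–83.9% under C.

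**Bias.** Let d be the completers' mean shift from the whole enrolled group, in SD units.
- Loss depends on the observed baseline value: the complete-case TBS − Baseline contrast is biased by −(1 − r)d; the mixed model is not.
- Loss depends only on a stable personal trait that does not alter the response to TBS: the trait cancels in the complete-case difference, so bias is 0. The mixed model with Baseline-only partial data is biased by (1 − r)d.

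A simulation with 25% loss, r = 0.5, no true effect, and logistic loss with slope 1 per SD of the driver gives:

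| Loss driven by | Complete cases, iTBS − Baseline | Mixed model, iTBS − Baseline |
|---|---|---|
| Observed baseline | 0.11 SD | 0 |
| Stable trait | about 0 | −0.08 SD (pattern B), −0.02 SD (pattern C) |

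The 0.11 corresponds to d = −0.11/0.5 = −0.22. For iTBS − cTBS, bias is about 0 by either method in these cases.

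**The case against.** The strongest reply is that the plan over-enrols precisely so that 30 complete datasets remain, which matches the N in Section VII. This stands: the planned number is met after the losses, so nothing here shows the trial falling short of its own target.

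A reader might infer that ten participants' data will be thrown away when a mixed model would keep them. The documents do not support that.
- Ten is an enrolment allowance, not a forecast. The compliance above 95% cited under Participant Retention suggests fewer losses, although that figure comes from questionnaire response.
- Losses could fall before any usable scan. Pregnancy and alcohol checks are repeated at Baseline, and TBS is targeted from the baseline scan. The compensation budget of $8,550 is exactly 30 × $285. Ten people paid for training, Baseline and one TBS visit would add up to 10 × ($55 + $60 + $85) = $2,000. This does not prove early loss, but nothing in the documents supports pattern C over the others.
- Complete-case deletion is inferred from the named method; it is not stated.
- Each outcome has its own ANOVA. A scan spoiled by movement need not remove that person's IC accuracy or SRT time, and no model can restore that scan's connectivity value.

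A reader might also infer that the complete-case result is valid only if loss is completely at random. That is too strong: under loss driven by a stable trait, the within-person contrast is unbiased and the mixed model is the one slightly off. Neither method is better under every mechanism.

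**Conclusion.** The point holds as an analysis choice worth changing. The named method drops incomplete participants outcome by outcome, the plan allows for up to 10 of 40 of them, and no other rule is given for Aims 1 and 2. The gain from a mixed model runs from none (no usable sessions), through 3.75–8.75% of variance for TBS versus Baseline and 0% for iTBS versus cTBS (Baseline only), to about 17–18% and 9–11% (Baseline plus one TBS visit, split 5/5). These figures rest on compound symmetry, an assumed correlation of 0.3–0.7 and exactly 10 incomplete participants. On bias, the mixed model protects against loss that depends on observed earlier sessions; it does not cure loss driven by unrecorded factors. The case for change is that it can only add usable information, costs little, and is of a kind the plan already uses for its exploratory spectroscopy outcomes.

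**What to change.** In the Aim 1 and Aim 2 analysis plans of Section VII, make the primary analysis of each outcome a linear mixed model fitted by REML with Kenward-Roger or Satterthwaite degrees of freedom:
- fixed effects for Condition (Baseline, iTBS, cTBS) and TBS period;
- a random subject effect;
- every participant with at least one usable value for that outcome.

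Code TBS period only within the TBS visits (for example −½ and +½ for the first and second TBS visit, 0 at Baseline). Baseline is always the first session, so a three-level visit factor would be confounded with Condition.

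Report the complete-case repeated-measures ANOVA as a sensitivity analysis. Under Missing Data and Attrition, state the analysis set for each outcome, the missing-at-random assumption, and that missing sessions will be tabulated by visit and reason. Reconcile N = 30 in Section VII with N = 40 in Section XII.

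The cost is SAP wording; no extra participants, visits or data are needed. The downside is small: TBS-versus-Baseline estimates can be slightly biased if loss follows an unobserved stable trait, and disagreement with the complete-case analysis would help to show this.
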